Some programs do the screening, refraction testing and provision of spectacles to children entirely in the school setting ("School Model"). One strength of such programs are that most children at school who need spectacles get them. However, sustainability is poor, because spectacles cannot be sold in many schools and there may be too few refractionists to cover all schools in most countries. Other programs provide vision screening at schools, but refer children who fail vision screening to nearby facilities for refraction and distribution/sale of spectacles ("Referral Model"). This model's strengths include lower demand on refractionists and opportunities for the spectacles to be sold. However, a disadvantage is that most of the referred children do not attend the specialist facility. One way to improve this might be to enhance the Referral Model and a recent USAID review by [name] and [name] showed that involving teachers in vision screening and family counseling significantly increases children's use of spectacles. Therefore, at 141 schools in India, involving over 42,300 children (assuming a minimum of 300 children/school), the investigators will study an "Improved Referral Model," with strong teacher involvement, to investigate the potential benefits of combining the lower costs of the "Referral Model" with the high uptake of the "School Model". The investigators will also assess the effects of allowing parents to purchase enhanced spectacles, rather than having their child use the free spectacles. Children will be randomized by school to the "School Model," "(Improved) Referral Model" or the "(Improved) Referral Model + Cost Recovery (sale of "upgrade spectacles" alongside offering free spectacles. The main study outcome will be program cost-effectiveness, defined as the program cost per child identified with correctable refractive error, who receives spectacles, and wears them at an un-announced visit 3 month after distribution. Profit on spectacles sold in the "Referral + Cost Recovery" group will be subtracted from the program costs in this study group. The groups will be compared, with and without adjustment for baseline characteristics.

Detailed Description:

Background

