Potential superiority of optimized Referral Models and improvements for vulnerable children: Recent evidence from a review by [name] and [name][11,12] and trials by [name][13] suggest that various strategies which increase involvement of teachers in the screening process (parent-teacher meetings; short message service (SMS), phone call, or handwritten notes in the students diary from teachers to families who do not complete referrals) can significantly increase the proportion of families following up for care at an outside eye care facility. Therefore, this cluster randomized trial will test an "optimized" model of distribution of spectacles, maximizing teacher involvement, to determine whether this approach can achieve comparable service uptake to fully school-based models at a greater level of cost-effectiveness. High-quality, trial-based evidence that showed that optimized Referral models are both low-cost and high-coverage may provide a strong stimulus to scale up refractive service programs in India and other low-middle income countries (LMICs). These programs can benefit millions of low-income children not currently receiving refractive services, thus improving their access to classroom learning.

This trial will compare two general screening methods: 1. School model and 2. Referral Model. A "Cost model", which is builds on the Referral model but includes the sale of spectacles, will also be included, as a third randomized group. In the School model, refraction occurs at the school and spectacles are given to children at the school, which may yield a higher rate of compliance, but is more expensive and may not be sustainable. On the other hand, the Referral model, where the children are referred to be screened at the vision center or service center may have lower compliance but be less expensive and more likely to be sustainable. This study examines the hypothesis that greater teacher involvement in screening and follow up can improve the compliance of children and families with the examination at the service center in the Referral model. For this reason, the main outcome of the trial is cost-effectiveness (amount spent per child who receives spectacles that improve his/her vision, and which are worn at an un-announced examination three months after distribution). If the teacher intervention can improve compliance in the Referral model,

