Sample size: At a refractive error prevalence of 3%, with minimum of 300 children/school, 95% of children receiving spectacles in the School Model, 40% of children wearing them in both the School Model and Referral Model groups at un-announced 3 month visits, a cost of US\$1.30 per child screened in the School Model and US\$0.80 in the Referral Model (all assumptions based on REACH Program data), if 58.5% of families accept referral to receive refraction and spectacles in the Referral Model, this would reach the same cost-effectiveness as the School Model. A total of 141 schools (47 in each of three groups) across three participating hospitals would be sufficient to detect significantly better cost-effectiveness of the Referral Model if 65% of families accept referral for refraction/spectacles, which is the target in our hypothesis; with a power of 90%, an alpha-error of 0.05, and an intracluster correlation coefficient (ICC) (a measure of how similar children are to one another within schools: "clustering") of 0.20.

Randomization: An independent statistician having no contact with participants will generate the randomization sequence using a computer system that is inaccessible until after the school has agreed to join the trial. Schools will be stratified into two groups as Public and private. The schools in each stratified group will be randomly assigned to either the intervention (referral models) or control group (school model) in a 1:1:1 ratio with a block size of three to ensure balance. After randomization, the schools and the children in them will not be masked to their allocated intervention but staff assessing data for the main outcome will not know a child's group assignment.

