Data to be acquired at baseline: Child: Age, gender, spectacles ownership, presenting and best corrected visual acuity in both eyes; refractive error in both eyes; distance of child's home from nearest Vision Center; brief spectacle attitude questionnaire; brief family Socio-Economic Status (SES) questionnaire[15]. Teacher: Brief questionnaire on attitudes and knowledge towards spectacles. Program: Survey of all program costs for screening and distribution for each model. Our cost-effectiveness analysis will be from the Program rather than the societal perspective, but the investigators will capture travel cost info from a 1% sample of randomly-selected children/families and capture information about teacher time spent in meeting with parents, sending notes to parents and encouraging children to wear spectacles in a 1 % random sample of Referral group teachers, in order to perform a sensitivity analysis of the impact of including these costs. Regarding programs costs, in the School model, where the optometrist team does the screening at school, the program

cost will be calculated by taking the cost of the primary and secondary screening, cost of the spectacles, and cost of delivering them. In the Referral model, the investigators will include the cost of primary screening, secondary screening at the vision centres and the cost of spectacles. In the Cost recovery model, the cost recovered by selling the spectacles (difference between retail price and cost of spectacles to the hospital) will be subtracted from the program cost. School: Urban versus rural, public versus private, size of the school, SES of community, and distance of the school from nearest Vision Center.

[figure not shown]
Follow-up schedule and follow-up data: Self-reported and observed spectacle wear to be ascertained at an un-announced follow-up at school 3 months after distribution of spectacles. Additionally, the following data for the Referral groups will be collected from the referral centre and verified from the children in a random sample of 10% of children: Did they visit the referral centre? Did they receive free spectacles? Did they elect to purchase upgrade spectacles? (in the Cost Recovery group). Children in the Referral groups not having received spectacles at the referral centres will receive them now, and so their visual acuity with spectacles and refractive power in each eye will be measured and recorded.

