Data collection: An experienced project coordinator will be responsible for data collection and follow-up. The project coordinator will be thoroughly trained on the completion of the data collection forms.

Data Management Plan: The baseline data will be entered and stored in the database (“Reachsoft”), which is password protected. Other data for the study will be collected and entered by an external data entry operator and sent to the project manager to store it in a password-protected system. The collected data will be analyzed in de-identified fashion by the study statistician in India.

A copy of the final study data will be shared with Queen's University Belfast (QUB) under the data sharing and protection outlined in a Memorandum of Understanding. The final dataset will be stored in the QUB database under QUB custody. The study team will have access to the data for research and analyses purposes only. Data will be stored for 5 years after the end of the study.

- **Study Flow:**

Data Analytic Plan: Data will be analysed using STATA 15. The primary and secondary outcomes will be compared between the three randomized groups using an intention to treat approach with and without adjustment for the baseline child, school and teacher factors listed above. Our primary outcome is cost-effectiveness (cost per child identified needing spectacles, who gets and is still wearing them 3 months later). The investigators have two hypotheses about this primary outcome:

Primary hypothesis: The improved Referral model which involves teachers contacting families will sufficiently improve uptake that this Referral model will be more cost-effective than the School model.

Proposed analysis: Cost per child identified needing spectacles (program perspective, as above), who gets and is still wearing them 3 months later, compared between School and Referral model.

Secondary hypothesis: Cost recovery from the Referral + Cost Recovery Model will make this more cost-effective than either of the other models.

Proposed analysis: Cost per child identified needing spectacles, who gets and is still wearing them 3 months later, compared between the Referral + Cost Recovery and other groups.

The investigators will also do a stratified analysis comparing the main outcome between groups at each of the 3 participating hospitals. Additional stratified analyses / balancing of the main outcome between groups will be done for public versus private schools and rural versus urban schools.

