Program cost-effectiveness

Program cost per child identified with correctable refractive error, who receives spectacles and wears them at an un-announced visit 3 month after distribution. Income from sales of spectacles in the "Referral + Cost Recovery" group will be subtracted from the program costs. The groups will be compared, with and without adjustment for baseline characteristics.

[Time Frame: 13 months]

Secondary Outcome Measures:

Proportion of children receiving spectacles who are wearing them at the time of un-announced 3-month follow-up

Purchase rates of upgrade spectacles in the Referral + Cost Recovery Group

Teacher and student reports of rates of teacher interventions in the two Referral groups (contact of parents to complete referral, encouraging children to wear spectacles)

Baseline visual acuity with spectacles

Refractive power of spectacles

[Time Frame: 12 months]

Eligibility

Minimum Age: 10 Years

Maximum Age: 15 Years

Sex: All

Gender Based: No

Accepts Healthy Volunteers: No

Criteria:

Inclusion Criteria:

Eligibility: Enrolment criteria:

- Children in randomly-selected 6th to 10th grades in selected schools with presenting visual acuity (that is, wearing spectacles if spectacles are owned at baseline) $\leq 6/9.6$ (0.2 LogMAR) in either eye.
- Children who already own spectacles will be requested to bring their spectacles on the day of screening, and children whose vision with existing spectacles meets study criteria will be eligible.
- Entry into the trial only requires that a child fail vision screening, which is assessed in the same way for all three randomized groups.

Exclusion Criteria:

- Parents returning the form indicating they do not wish their child to participate;
- no Vision Center within 50 km of the child's home (a rare occurrence in the REACH network).
- If the child is incapable of completing visual acuity screening in both eyes for any reason.

References

Citations:

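### The sales offset for the Cost Recovery arm is income in one place and margin in two others, and the plan does not say whether sold pairs' purchase cost is already in programme cost

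*Combined protocol and SAP*

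**What the plan says.** Three current statements describe what is taken off the cost of the Referral + Cost Recovery arm:

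- Opening summary: "Profit on spectacles sold in the 'Referral + Cost Recovery' group will be subtracted from the program costs in this study group".
- Data to be acquired at baseline, programme costs. The recovered amount is defined as a margin: "difference between retail price and cost of spectacles to the hospital) will be subtracted from the program cost".
- Outcome Measures, Primary Outcome Measure: "Income from sales of spectacles in the 'Referral + Cost Recovery' group will be subtracted from the program costs". The term is not defined there.

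The costing text lists components for the School and Referral models. For the Referral model, "the investigators will include the cost of primary screening, secondary screening at the vision centres and the cost of spectacles". For Cost Recovery it gives only the offset. It also promises a survey of all screening and distribution costs for each model, but does not mention sold pairs. The Background describes the third arm as one "which is builds on the Referral model but includes the sale of spectacles".

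The offset feeds the secondary hypothesis in the Data Analytic Plan: "Cost recovery from the Referral + Cost Recovery Model will make this more cost-effective than either of the other models".

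**The concern.** Profit and margin are net of what the hospital paid for the spectacles. Income from sales, on its plain reading, is gross. The two differ by the purchase cost of every upgrade pair sold.

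Aligning one word would not settle the matter, because the right offset depends on the cost base. Since the third arm builds on the Referral model, and the Referral list includes spectacles, a reader could reasonably put the purchase cost of sold pairs into programme cost. The margin rule would then charge it twice. A reader who costs sold pairs only through the margin leaves it out of programme cost, and the income rule would then never charge it.

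The offset is one component of this arm's cost per wearer, alongside attendance and wear, and it is the mechanism that the secondary hypothesis names. As written, the numerator could be settled after sales are known.

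**Working it through.** **The plan's own figure.** The only cost-effectiveness result stated is the break-even referral acceptance of 58.5% (Sample size). From the inputs there (95% receipt in the School Model, $1.30 and $0.80 per child screened, equal wear): 0.95 × 0.80 / 1.30 = 58.46%, which agrees. With 3% prevalence and 40% wear, cost per wearer is:

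- School: 1.30 / (0.03 × 0.95 × 0.40) = $114.04
- Referral at 65% acceptance: 0.80 / (0.03 × 0.65 × 0.40) = $102.56
- Difference: $11.47 (from unrounded values)

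These give a scale only. The documents state no expected figure for Cost Recovery.

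**The four readings.** Let F be all other cost in the arm, R the sales receipts and C the purchase cost of sold pairs. The margin is R − C. The worked column assumes 100 recipients, 30 buyers, purchase cost $2, retail price $4 and 40 wearers, so R = $120, C = $60 and the margin is $60.

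| C in programme cost? | Subtracted | Net cost | Worked | Error |
|---|---|---|---|---|
| Yes | Receipts | F + C − R | F − 60 | none |
| No | Margin | F − (R − C) | F − 60 | none |
| No | Receipts | F − R | F − 120 | too low by $60 |
| Yes | Margin | F + C − (R − C) | F | too high by $60 |

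The first two rows are the same number. The last two are wrong by C in opposite directions, here $60 / 40 = $1.50 per wearer each way and $3.00 apart. So, with income read as receipts, one of the two stated offsets is wrong whichever cost base is used.

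**Size.** Error per wearer = (share of recipients buying × unit purchase cost) / wear rate. Retail price cancels. The plan gives no purchase share or unit cost, and its wear assumption covers only the other two arms: "40% of children wearing them in both the School Model and Referral Model groups". All rows below are therefore assumptions.

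| Share buying | Unit cost | Wear | Error per wearer | Distance between the two wrong readings |
|---|---|---|---|---|
| 10% | $1 | 40% | $0.25 | $0.50 |
| 30% | $2 | 40% | $1.50 | $3.00 |
| 50% | $5 | 40% | $6.25 | $12.50 |
| 30% | $2 | 30% | $2.00 | $4.00 |
| 30% | $2 | 60% | $1.00 | $2.00 |

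Against the Referral figure of $102.56, the three 40%-wear cases are about 0.2%, 1.5% and 6.1%.

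**Could the ranking change?** Assume 30% buying, $5 unit cost, $8 retail, 65% uptake, 40% wear, and $0.80 per child screened as the cost before any sold pairs. Per recipient, receipts are 0.30 × 8 = $2.40, the margin is 0.30 × 3 = $0.90 and purchase cost is 0.30 × 5 = $1.50. Dividing each by 0.40 gives $6.00, $2.25 and $3.75 per wearer.

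- Cost excluded, receipts subtracted: 102.56 − 6.00 = $96.56
- Either consistent reading: 102.56 − 2.25 = $100.31
- Cost included, margin subtracted: 102.56 + 3.75 − 2.25 = $104.06

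The last figure is above Referral's $102.56 and the others are below it. This depends on giving no credit for free pairs that buyers do not take. If the $0.80 includes free pairs, a saving of $2 on each lowers the last figure by 0.30 × 2 / 0.40 = $1.50, to $102.56, and a larger saving removes the reversal.

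**The case against.** The strongest reply is that the costing text is the only place that explains how costs are calculated. It defines the offset as a margin, and the summary agrees. Income in the outcome definition may simply be loose wording for profit, and a general term should be read through the specific one. Costing sold pairs only through the margin is an ordinary use of a margin and is internally coherent. On that view a rule is already specified, and the double count is an inference that no sentence states.

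Much of this is fair. The costing text is coherent on that reading, and no miscalculation has been shown. But the outcome definition does not refer back to the margin, and even if it did, nothing says that sold pairs are kept out of programme cost. The promised survey of costs for each model does not settle it. If that survey captures sold pairs, receipts are the correct offset and the margin is the wrong one.

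It is also fair that the dollar sizes are almost wholly assumed and span a 25-fold range, that the doubled figures compare two wrong readings with each other rather than with the truth, and that the ranking change is fragile. They show what could happen and are not forecasts.

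**Conclusion.** The concern holds. The formal primary outcome and the costing text state offsets that differ if income means receipts, and the cost base needed to choose between them is not specified. The conflict in wording and the accounting identity do not rest on assumed inputs. The dollar size does: about $0.25 to $6.25 per wearer across the cases at an assumed 40% wear.

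The effect is confined to the Cost Recovery arm, and so to the secondary hypothesis and any other comparison using that arm's cost. The primary School versus Referral comparison and the sample size do not use the offset. This should be corrected before sales data are seen, but it does not threaten the main comparison.

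**What to change.** In the Primary Outcome Measure, replace income with the margin already defined in the costing text. In the costing text, add one clause: the purchase cost of sold upgrade pairs is excluded from Cost Recovery programme cost because it is already netted in the margin. The summary's use of profit then agrees.

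An equivalent rule is: net Cost Recovery cost = the components listed for the Referral model, with the purchase cost of all pairs dispensed (free and upgrade) counted once, minus sales receipts. Either form is valid if used throughout. Report sales receipts and purchase cost on separate lines so that readers can check the result.

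The cost is one word and one clause. No new data are needed: the margin already requires retail price and purchase cost, and upgrade purchase rates are already a secondary outcome.
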